 We will recruit 400 participants between Mount Sinai and University of Colorado.

d) Study Timelines:

- *If not in the protocol, please clarify the how long an individual subject may be in the protocol, and for how long the protocol will be active at Mount Sinai.*

Describe:

- *The duration of an individual subject's participation in the study (including follow-up).*
 Subjects will participate in the study for 18 months. If they are eligible to enroll in the pilot, subjects will participate for an additional 8 weeks.
- *The duration anticipated to enroll all study subjects.*
 We will enroll all subjects in 2.5 years.
- *The estimated date for the investigators to complete this study (complete primary analyses)*
 5 years

The study will take place from April 11, 2016 to August 28, 2021. The end date is 120 calendar days after the end of the period of performance, as per the NIH Final Progress Report Guidelines.

e) Specimen Banking for Future Uses Not Part of This Project:

- *If storage will be occur at Sinai and elsewhere (e.g. the sponsor) be sure to answer these questions for both sets of samples as, at the very least, governance of future uses will differ.*

See below answers.

- *If specimens will be banked for future use, describe:*

Specimens will be banked for future ADMA and L-arginine analyses.

- *Where the specimens will be stored, what access controls and security systems will be in place?*

The specimens will be stored in [name] laboratory in the Icahn Medical Institute at [name] [REDACTED]. The specimens will

 Mount Sinai	Protocol Name:	Obesity and Asthma: Unveiling Metabolic and Behavioural Pathways
	Principal Investigator:	[name], DrPH
	Primary Contact Name/Contact Info:	[name] / [contact] / [contact]
	Date Revised:	1/25/21
	Study Number:	STUDY-16-00079

be stored in -80 degree freezer and locked securely to minimize the risk of a breach of confidentiality. Specimens will then be shipped to [name] lab at the Hospital for Sick Children on the 9th floor of SickKids new research facility, the Peter Gilgan Centre for Research and Learning (PGCRL). The specimens will be stored in freezer and locked securely to minimize the risk of a breach of confidentiality

- *How long they will be stored?*

Samples will be stored indefinitely.

- *How will researchers gain access to the specimens? If there is a resource utilization committee please provide a description.*

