The primary asthma morbidity outcomes will be FEV1 and control (ACQ scores); the primary measure of NO metabolism will be L-arginine/ADMA ratio. All analyses will compare four groups: 1) obese with late onset asthma; 2) obese with early onset asthma; 3) non-obese with late onset asthma; and 4) non-obese with early onset asthma. First, we will compare the levels of plasma L-arginine, ADMA, L-arginine/ADMA ratios, and arginase among these groups, at each time point using the Kruskal-Wallis test. The Wilcoxon signed-rank test will be used to compare levels of NO metabolism biomarkers in periods without vs. during asthma attacks. The analysis will involve longitudinal assessment of asthma morbidity measures across four time points (0, 6, 12, and 18 months). We hypothesize that both time-varying covariates (e.g., NO metabolism biomarkers) assessed at the four time points and time-invariant covariates (e.g., early vs. late asthma onset) will predict asthma morbidity assessed at these time points (Figure 1). We also hypothesize potential lagged effects of covariates at earlier time points. As a first step, we will identify the measurement model for the latent variables at each time point using confirmatory factor analysis. Specifically, we will create latent variables representing random effects intercepts and slopes for NO metabolism (NOt0, NOt6, NOt12 and NOt18; where t0 represents baseline NO metabolism biomarkers) and asthma morbidity measures (AMt0, AMt6, AMt12 and AMt18; e.g., FEV1 at baseline, 6, 12, and 18 months). We will estimate slope and intercept parameters using a Weighted Least Squares Mean-Variance adjusted (WLSMV) estimator, which provides robust estimates for complex models with modest sample sizes and can be employed with dichotomous, ordinal, and/or continuous endogenous variables. We will test this measurement model for absolute fit using Chi-square and RMSEA statistics. In addition, we will consider adjusting the model based on modification indices to improve the overall fit.

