Next, an overall unconditional model will be fitted to identify the growth trajectory across time. To that end, we will fit a growth function for NO metabolic biomarkers and asthma morbidity (e.g., FEV1) using linear, quadratic, and unstructured models. Relative model fit will be evaluated based on various indices of exact and close fit:  $\chi^2$  (>.05), the comparative fit index (CFI>.97), the Tucker-Lewis fit index (TLI>.97), the root mean squared error of approximation (RMSEA<.05), and the weighted root mean square residual when using WLSMV (WRMR<.90). The most parsimonious model with the best fit will be retained. Finally, we will fit the full structural model, including the hypothesized relationships. For example, obesity and age of onset will be included as a predictor of NO metabolism-related pathways as well as asthma morbidity. Because we hypothesize that NO metabolism-related pathways are primarily important for obese patients with late onset asthma, we will include an interaction term between obesity and age of asthma onset. The model will also control for sex, age, comorbidities (including OSA), depression, allergic sensitization, and other key baseline covariates. To address the possible mediational effects of NO metabolism-related pathways, we will fit models to estimate both direct and indirect effects, first separately, and then combined. Lagged effects of the time- varying predictors, as well as the effects of the latent growth variables themselves (intercept, slope, and their random effects) will be evaluated as potential mediators (i.e., NO metabolism biomarkers) of the effects of obesity and age of onset on asthma morbidity. We will also be able to compare models of complete vs. partial mediation by comparing constrained models (direct effects constrained to zero) with unconstrained models that allow for partial mediation. Relative fit, as well as estimates of effect size will be calculated, along with Sobel tests and Monte Carlo confidence intervals to evaluate the mediational hypotheses. As indicated above, the interrelationships between gender, obesity, and asthma morbidity is complex, thus, we will explore the potential modifying effects of gender. We will also conduct sensitivity analyses in which we test different thresholds for the definition of good medication adherence (≥70%, 60%, 50%). Once the final model is fitted, we will repeat the analyses freeing the parameters to differ by gender. Comparing these models to a model in which the differential effects of gender are constrained will provide valuable insight into the possible role of

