We will use LGCM to examine the interrelationships between asthma- and obesity-related beliefs and self-management of these conditions over time (Figure 4). Latent variables to be investigated include: 1) cognition, as measured by the battery described above; 2) asthma beliefs; 3) obesity beliefs. Asthma and obesity beliefs will constitute a latent variable consisting of two constructs: a) disease beliefs (measured with the IPQ) and b) medication/diet/exercise beliefs (measured with the BMQ); and 3) asthma and obesity SMB, including time-variant medication adherence (electronic and self-report measures following each study time point), diet, exercise and other SMB. We will use LGCM to predict the effects of obesity on these latent behavioral constructs. We will be able to examine the direct and indirect pathways from obesity to cognitive functioning and illness beliefs, to asthma and obesity SMB (intercept, slope, as well as their random effects). We will assess the potential influence of cognition and illness beliefs on SMB separately then test a full model, predicting SMB once individual contributions are identified. As in Aim 1, we will estimate both direct and indirect effects, as well as partial vs. complete mediation. We will include covariates as above. Integrating Biological and Behavioral Pathways: Finally, we will employ LGCM to characterize the interrelation and relative contribution of biological and behavioral pathways linking obesity and asthma morbidity (Figure 1). In addition to the time-variant relationships between SMB and biological markers, we will also explore the possibility of time-lagged relationships between biological markers and SMB. For example, we will assess if SMB at time 1 predict L-arginine/ADMA ratios at time 2, and vice-versa. Comparison of model fit among these lagged analyses will yield critical new data to elucidate the complex interplay between biology and behavior in the maintenance of asthma morbidity. The model will control for other confounders as specified above.

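### With visits six months apart and no calendar-season term, an annual cycle shared by the NO biomarkers and morbidity or self-management could create a same-visit association and an opposite-signed six-month lag

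*SAP*

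**What the plan says.** SAP, Aim 1 describes a "longitudinal assessment of asthma morbidity measures across four time points (0, 6, 12, and 18 months" and takes as predictors "time-varying covariates (e.g., NO metabolism biomarkers) assessed at the four time points". It adds: "We also hypothesize potential lagged effects of covariates at earlier time points". Lagged effects and the latent growth variables "will be evaluated as potential mediators (i.e., NO metabolism biomarkers) of the effects of obesity and age of onset on asthma morbidity".

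The candidate growth functions are linear, quadratic or unstructured, all in study time. The adjustment set is: "The model will also control for sex, age, comorbidities (including OSA), depression, allergic sensitization, and other key baseline covariates".

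SAP, Aim 2 (the paragraph on integrating biological and behavioural pathways) adds lags between self-management behaviours (SMB) and the biomarkers: "we will assess if SMB at time 1 predict L-arginine/ADMA ratios at time 2, and vice-versa". On adjustment it says: "The model will control for other confounders as specified above".

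Protocol section 3d (Study Timelines) says: "We will enroll all subjects in 2.5 years". Neither document names season, calendar month, pollen or visit date as a model term.

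**The concern.** A patient first seen in one season is next seen in the opposite one, then back in the first, then the opposite again. The shortest lag the design allows is six months, which is always the opposite season. The named adjustments are patient traits or baseline values. Entered with a constant effect, such terms cannot remove a swing that alternates within the patient. Growth functions in study month cannot do so either when start dates are spread over 2.5 years, because a given study month then falls in every season.

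The exposed results are the same-visit and lagged paths, the NO-to-morbidity leg of the mediation model, and the covariances between individual slopes. They support the plan's statements about mediation and about whether biology leads behaviour or the reverse. A positive same-visit path with a reversed lag could be read as a substantive finding, and the analysis as written could not tell it from the calendar.

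**Working it through.** **Inputs.** Visits at 0, 6, 12 and 18 months (SAP, Aim 1). Enrolment over 2.5 years (Protocol 3d), taken as uniform. N = 400 × 0.80 = 320 (SAP, Power Calculation). The documents give no seasonal amplitude, so it is an assumed range. Let *a* be the cosine amplitude in units of the non-seasonal within-patient SD. Both series have the same amplitude and phase, and the true effect is zero.

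**The plan's own figure.** There is none for season. The nearest is the Aim 1 power statement (above 0.80 for an average effect of 0.10), which rests on RMSEA 0.05 against 0.03. With noncentrality (N−1) × df × RMSEA² and N = 320, power reaches 0.80 at df ≥ 99 (0.807 at df = 100). There are 34 × 35 / 2 = 595 variances and covariances, so such a df is plausible. The model df is not stated, so the figure is consistent with its inputs but cannot be reproduced.

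**Step 1, sign.** With *t* in years, cos(2π(t + 0.5)) = −cos(2πt). The seasonal covariance is +a²/2 at the same visit and −a²/2 one visit apart.

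**Step 2, pooled correlation.** r = ±(a²/2) / (1 + a²/2). For a = 0.3: 0.045 / 1.045 = 0.043.

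**Step 3, same-visit slope with person effects removed.** Centring on four visits removes a quarter of the noise variance but none of the alternating cycle: slope = (a²/2) / (a²/2 + 0.75). For a = 0.3: 0.045 / 0.795 = 0.057.

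**Step 4, false positives.** The standard error is about 1/√(320 × 3) = 0.0323. The two-sided 5% rejection rate is Φ(z − 1.96) + Φ(−z − 1.96), with z = slope / 0.0323.

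| a | Pooled r, same visit / one-visit lag | Person-centred same-visit slope | False-positive rate, formula | Simulation |
|---|---|---|---|---|
| 0.1 | +0.005 / −0.005 | +0.007 | 5.5% | 7% |
| 0.2 | +0.02 / −0.02 | +0.026 | 13% | 13% |
| 0.3 | +0.04 / −0.04 | +0.057 | 42% | 44% |
| 0.42 | +0.08 / −0.08 | +0.105 | 90% | 90% |
| 0.5 | +0.11 / −0.11 | +0.143 | 99% | not listed |
| 0.6 | +0.15 / −0.15 | +0.194 | about 100% | not listed |

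At a = 0.1 the rate is near the nominal 5%.

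**Step 5, individual slopes.** With time coded −1.5, −0.5, 0.5, 1.5, the least-squares slope of +a, −a, +a, −a is (−1.5a + 0.5a + 0.5a − 1.5a) / 5 = −0.4a per six-month interval. The sign is opposite for patients enrolled half a year apart, so the mean slope is hardly affected, but slopes of two seasonal series become correlated: r = 0.08a² / (0.2 + 0.08a²), which is 0.03 at a = 0.3 and 0.13 at a = 0.6.

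**Step 6, lagged path and limits.** A separate simulation (500 replicates, N = 320, visit-date SD 0.5 month, total within-patient SD 1) set the SD of the cycle at 0.3. That is an amplitude of 0.3 × √2 = 0.42, so it belongs beside the 0.42 row.

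| Setting | Same-visit slope (false positives) | Six-month lagged slope (false positives) |
|---|---|---|
| No seasonal term | +0.116 (93%) | −0.086 (76%) |
| Concurrent biomarker and prior morbidity also in the lag model | – | −0.073 (62%) |
| Peaks 1.5 months apart | +0.084 (74%) | −0.063 (49%) |
| Peaks 3 months apart | none (7%) | none (5%) |
| Only the biomarker seasonal | none (5%) | none (6%) |
| Visit-date SD 1.5 months | +0.106 (89%) | −0.055 (43%) |
| Sine and cosine of visit date added | +0.001 (5.6%) | −0.001 (6.6%) |

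Baseline season entered with one constant effect left the pooled same-visit slope at +0.091 and the lagged slope at −0.077.

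**The case against.** The strongest reply is that the size is assumed. The documents report no seasonal swing in L-arginine/ADMA, FEV1, ACQ or SMB. An amplitude of 0.5 SD means a full 1 SD from peak to trough in both series, and nothing in the documents supports that. At 0.1 SD the effect is negligible, and it vanishes if only one series is seasonal or the peaks are three months apart. All of this stands, and it makes the point conditional.

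Second, the covariate list is open-ended, and a baseline variable in a structural equation model may have wave-specific effects. Sine and cosine of enrolment date, with a separate path to each wave, cut the spurious same-visit slope at amplitude 0.5 from 0.14 to about 0.00–0.01. So the framework can hold the remedy, but the SAP does not specify it.

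Third, the lags are described as possibilities to explore. That lowers the stakes for those paths but does not protect the same-visit path or the mediation leg.

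Fourth, under exactly six-month spacing, sine and cosine at four waves are eight covariates of rank 2. With 0.5-month date variation the waves still correlate at about 0.93 in absolute value. Free coefficients at every wave, plus interactions, would be costly. This stands, and it shapes the fix.

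A reader might infer that Aims 1 and 2 are compromised as a whole. The documents do not support that. Aim 1 compares four groups defined by obesity and age of onset. Those contrasts, and the obesity/onset-to-NO leg, are not biased by season if enrolment season is balanced across groups. Aim 2's adherence comparison is a chi-square test by category. A reader might also infer that season could supply the whole 0.10 effect in the power statement. The SAP defines effect size through RMSEA and gives that 0.10 no metric, so the two cannot be compared.

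**Conclusion.** The concern holds as a conditional weakness. The six-month spacing, the same-visit and lagged paths, and the absence of any stated calendar term are all in the text, and the sign reversal follows from them. Whether it matters depends on three things the documents do not settle: that both series are seasonal, that their peaks are not about three months apart, and that the amplitude is well above 0.1 within-patient SD. Under a shared phase and no true effect, the same-visit false-positive rate at N = 320 runs from near nominal at 0.1 to about 13% at 0.2, 44% at 0.3 and 90% at 0.42.

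The exposure is confined to the within-patient same-visit and lagged paths, the NO-to-morbidity leg, and slope covariances. The calculations use regressions in place of the planned WLSMV growth model, so they show direction and order of size, not the exact bias. The documents do not show that season will distort these paths, only that the stated analysis could not rule it out.

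**What to change.** At each site, compute sine and cosine of day-of-year from every visit date. Add both to the Aim 1 structural model and the Aim 2 models as time-varying covariates, acting on the NO indicators and on the morbidity or SMB indicators. Hold their coefficients equal across waves: this adds two parameters per series and avoids the rank problem of wave-specific terms. Report the same-visit and lagged paths with these terms, and show the unadjusted paths alongside. Interactions with site or allergic sensitization are optional.

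The cost is a few parameters (two series × two terms = four for one biomarker and one outcome). Visit date, or the two derived terms, must also be carried into the analysis file. Protocol section 3f says that data sent to the coordinating centre are de-identified, and the documents do not say that visit dates are in that file, so deriving the terms at the site is the simpler route. If the seasonal amplitude proves trivial, the two sets of estimates will agree and the report can say so.

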Obesity and Asthma: Unveiling Metabolic and Behavioral Pathways

Statistical Analysis Plan

PI: [name], DrPH

NCT04113746

Document Date: 8-12-2015

**Data Analyses:** We will obtain a HIPAA waiver to use de-identified data to compare non-respondents and those lost to follow-up to study participants by age, gender and ethnicity. **Factor Structure of Measures:** We will examine the factor structure of key measures (e.g., MARS) and the multi-component structure of the IPQ and BMQ. **Measurement Invariance:** We will determine whether the key measures are invariant across language using multiple indicator multiple cause models. We will use the chi-square test, ANOVA, or the Kruskal Wallis test to compare the baseline characteristics of obese vs. non-obese patients with early onset and late onset asthma, as appropriate. **Overview:** We will employ latent growth curve modeling (LGCM) approaches using MPLUS 7.3 software to test Aims 1 and 2 hypotheses. LGCM leverages the analytical power of structural equation modeling (SEM) for the intensive analysis of longitudinal data. Similar to classic SEM, LGCM allows for the examination of complex models including those that posit mediation and moderation, as proposed here. Before conducting analyses, we will examine the distribution of dependent variables and, as appropriate, consider transformations (e.g., log, Box-Cox) to reduce non-normality in continuous variables.

**Aim 1.** Compare the longitudinal relationship between L-arginine/ADMA balance and morbidity (lung function, asthma control, acute resource utilization, and quality of life) between obese adults with late onset asthma vs. (1) obese adults with early onset asthma and non-obese asthmatics with early (2) or late (3) onset disease:

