**Missing Data:** For data missing at random (e.g., data entry errors), we will use multiple imputation methods with PROC MI and PROC MIANALYZE in SAS. For the outcome assessments, we cannot assume data are missing at random, but we will consider pattern-mixture methods to adjust for an occasional missed point in subjects who complete subsequent follow-up. **Power Calculation:** Power calculations for LGCM and sample size based were based on published methods. Effect size in this approach is defined as a null and alternative hypothesis value of the RMSEA index, which we hypothesize to be 0.05 (adequate fit) and 0.03 (good exact fit), respectively. Power in SEM can be conceptualized as a function of sample size and the number of parameters to be estimated in the model, relative to the information provided in the overall variance-covariance matrix of the observed variables. The estimated power is based on a proposed sample size of 400 with an 80% follow-up rate. For Aim 1, the proposed model involves 14 latent variables across all time points, and 34 observed underlying variables, yielding estimated power >0.80 for an average effect of 0.10 with an alpha of 0.05. For the model in Aim 2, there are 13 latent variables (not including the six separate indicators of cognition) and 18 observed variables, yielding >0.80 power for average effects of 0.15. Overall, despite the challenges of estimating *a priori* power for SEM approaches, especially those involving growth models, we believe the proposed study will be adequately powered to address the research aims.

**Aim 3.** Develop and pilot test three theory-based modules that integrate counseling for asthma and obesity to promote better SMB, including self-monitoring, adherence to asthma medications, and lifestyle changes for weight loss: **Overview:** We will script messages aimed to counter beliefs linked to low adherence to asthma and obesity SMB and to support those that promote better SMB. We will incorporate these messages in 3

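### Obesity's direct, indirect and relative pathway effects are estimated net of OSA, comorbidities and depression, some of which may be consequences of obesity, and no model without them is planned

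*SAP*

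**What the plan says.** The headline of Aim 1 in the SAP is: "Compare the longitudinal relationship between L-arginine/ADMA balance and morbidity", across four groups defined by obesity and age of onset. The same aim then sets up a structural model in which "obesity and age of onset will be included as a predictor of NO metabolism-related pathways as well as asthma morbidity". It adds that "we will include an interaction term between obesity and age of asthma onset".

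The adjustment is given as a single list: "The model will also control for sex, age, comorbidities (including OSA), depression, allergic sensitization, and other key baseline covariates". The Aim 1 mediation analysis concerns "potential mediators (i.e., NO metabolism biomarkers) of the effects of obesity and age of onset on asthma morbidity", so OSA, comorbidities and depression are not among the named mediators. Complete and partial mediation are distinguished by "comparing constrained models (direct effects constrained to zero) with unconstrained models that allow for partial mediation".

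Aim 2 takes over the Aim 1 covariates. Its closing paragraph, on integrating biological and behavioural pathways, sets out to weigh the routes linking obesity to asthma morbidity, and says: "The model will control for other confounders as specified above".

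The SAP text gives no causal role for OSA, comorbidities or depression. It does not say which equations they enter, and it describes no run without them. The sensitivity analyses in Aim 1 cover adherence thresholds, and the model is refitted to explore gender.

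**The concern.** A confounder of obesity's effect is a variable that influences both obesity and the outcome. A variable that obesity causes, and that itself affects morbidity, lies on the pathway. Conditioning on it removes that part of the obesity effect. OSA is the one comorbidity named, and it is the most plausible candidate. Depression and the unlisted comorbidities may be candidates in part.

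What is at stake is the interpretation of the mediation results. With NO as the only named mediator in Aim 1 and OSA held fixed, the direct effect being tested against zero has already lost any route through OSA. A direct effect near zero could then be reported as complete mediation by NO, although OSA carries part of the effect. The relative contribution of biological and behavioural routes in the integrated model has the same difficulty: the total being divided depends on the covariate list, and the SAP does not say so.

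**Working it through.** **The plan's own figure.** The only figure stated for the Aim 1 model is its power: "yielding estimated power >0.80 for an average effect of 0.10 with an alpha of 0.05". It does not bear on this point. With null and alternative RMSEA of 0.05 and 0.03 and noncentrality (N − 1) × df × RMSEA², power passes 0.80 once df is at least 71 at N = 400, or 99 at N = 400 × 0.80 = 320. The SAP does not state df, so the figure can be neither confirmed nor refuted.

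**Inputs.** The documents give no path values for OSA, comorbidities or depression. All values below are assumed, in standardised units, and illustrate the mechanism only.

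**Paths.** X is obesity, L a covariate, M the NO biomarker, Y morbidity. a1 = X→L, a2 = X→M, b = L→M, c = L→Y, d = M→Y, e = X→Y directly.

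- Total effect of obesity = e + a1·c + (a2 + a1·b)·d
- Effect left after adjusting for L = e + a2·d
- Removed = a1·(c + b·d)
- NO share of the total = (a2 + a1·b)·d / total
- NO share after adjustment = a2·d / (e + a2·d)

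**Results**, with a2 = d = 0.20 throughout:

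| Case | e | a1 | b | c | Total | Adjusted | Removed | NO share of total | NO share adjusted |
|---|---|---|---|---|---|---|---|---|---|
| A | 0.10 | 0 | any | any | 0.140 | 0.140 | 0% | 28.6% | 28.6% |
| B | 0.10 | 0.1 | 0 | 0.1 | 0.150 | 0.140 | 6.7% | 26.7% | 28.6% |
| C | 0.10 | 0.4 | 0.2 | 0.3 | 0.276 | 0.140 | 49.3% | 20.3% | 28.6% |
| D | 0.10 | 0.4 | 0.2 | 0.1 | 0.196 | 0.140 | 28.6% | 28.6% | 28.6% |
| E | 0.10 | 0.4 | 0.2 | 0.05 | 0.176 | 0.140 | 20.5% | 31.8% | 28.6% |
| F | 0 | 0.3 | 0 | 0.2 | 0.100 | 0.040 | 60.0% | 40.0% | 100% |

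B and C are the ends of a grid with e = 0.10, a1 from 0.1 to 0.4, b from 0 to 0.2 and c from 0.1 to 0.3. E and F lie outside that grid.

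**Complete mediation.** In F the total is 0.20 × 0.20 + 0.30 × 0.20 = 0.04 + 0.06 = 0.10, of which NO carries 0.04. After adjusting for L the direct effect is zero, so the constrained model fits and NO appears to carry everything.

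**Direction of the NO share.** With all paths positive, the adjusted share exceeds the true share when a2·c > b·e. D is the point of equality (0.20 × 0.1 = 0.2 × 0.10). In E the inequality reverses and adjustment understates the share.

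**Interaction.** If L acts equally in both onset groups, adjustment changes the obesity-by-onset contrast by the difference in a1 between late and early onset, times (c + b·d). It is zero when a1 is the same in both.

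**Dropping L altogether.** The estimated NO-to-morbidity path becomes d + c·b·(1 − a1²) / (1 − (a2 + a1·b)²). Over the grid with b > 0, a true 0.20 is estimated as about 0.21 to 0.26. For example, a1 = 0.1, b = 0.2, c = 0.3 gives 0.20 + 0.06 × 0.99 / 0.9516 = 0.262. Simple omission is therefore not a clean remedy.

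**The case against.** The strongest defence is that the adjustment suits what Aim 1 puts first. The headline target is the relationship of L-arginine/ADMA balance to morbidity by group. For that relationship OSA, comorbidities and depression may be needed as confounders of NO and morbidity, and the last calculation shows the bias from leaving them out. This stands. It does not cover the mediation analysis in the same aim, or the integrated model, which are about effects of obesity.

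The causal direction is also not in the documents. Obesity is a BMI category (Protocol, Recruitment Methods) and the covariates are baseline measurements, so no time order is recorded. Depression could run either way, and the comorbidities are not listed. The path diagram is not visible in the copy reviewed, and the SAP refers to material outside it that may hold a rationale. This stands too, and is why the point is conditional.

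Third, some unadjusted comparisons are planned: Kruskal-Wallis tests of the biomarkers by group and chi-square tests of adherence. They give neither an obesity effect on FEV1 or ACQ nor a mediation split.

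A reader might infer that these covariates are mostly consequences of obesity, so that the plan necessarily understates the obesity effect, overstates the NO share and distorts the interaction term. The documents do not support that. The NO share can move either way or not at all, and the interaction moves only if the obesity-covariate association differs by onset group.

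**Conclusion.** The point holds in conditional form. The SAP estimates direct, indirect and relative pathway effects of obesity while holding fixed variables that may partly result from obesity, and it plans no model that would show the difference. To the extent that obesity causes them, the estimates leave out those routes, and a finding of complete mediation by NO could be wrong.

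The size is unknown for this trial. About 7% to 49% of the total obesity effect is removed on the assumed grid, and 0% if obesity does not cause the covariate. The change from 40% to 100% in case F shows what can happen and does not predict it. These figures assume linear paths of the same sign. The point does not invalidate Aim 1's headline comparison. It is worth acting on because the change is cheap and the mediation conclusion is open to misreading without it.

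**What to change.** In the SAP, for every obesity effect and mediation split in Aim 1, Aim 2 and the integrated model, prespecify and report two models:

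1. Adjusted for sex, age and other covariates judged not plausibly caused by obesity, with the reason given for each, and read as the total obesity effect.
2. Adjusted for the full current list, and read as the effect not operating through OSA, comorbidities or depression.

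For the mediation split, keep OSA, comorbidities and depression in the NO-to-morbidity equation, or model OSA and depression as mediators in parallel with NO. An obesity path in an equation that contains OSA is still net of OSA. The total must therefore come from model 1, and the part not carried by NO is that total minus the NO-mediated part. This subtraction relies on the linear paths used above. State that complete mediation by NO will not be concluded from model 2 alone.

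The cost is SAP wording and one extra run per outcome, with no new data. The drawbacks are two obesity estimates to explain and possible residual confounding in model 1 if a dropped covariate is a true confounder.
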